3.2.4 Characteristics of children participating in the longitudinal survey

The same variables as those used for children participating in the HHS cross-sectional surveys will be described, with additional variables:

Variables	Modalities
Anthropometric data	
Weight	Quantitative and/or relevant classes
Length/Height	Quantitative and/or relevant classes
Weight for Length/Height z-score	Quantitative and/or relevant classes
Weight for age z-score	Quantitative and/or relevant classes
Length/Height for age z-score	Quantitative and/or relevant classes
Household hunger score	
Household hunger score	Quantitative
Household hunger score conclusion	Categories
Nutrition data	
Minimum dietary diversity score	Quantitative and/or relevant classes
Breastfeeding	Binary Yes/No
SQ-LNS supplementation	Binary Yes/No
SQ-LNS consumption during the previous 7 days	Quantitative and/or relevant classes
SQ-LNS sharing if SQ-LNS supplementation is yes	Categories
Reasons for sharing SQ-LNS if SQ-LNS sharing is yes	Categories
Seasonal malaria prevention treatment received	Binary Yes/No
Months when Seasonal malaria prevention treatment was received	Categories
Cost-effectiveness	

3.3 BASELINE RESULTS DESCRIPTION

At the end of the HHS baseline cross-sectional survey, all primary and secondary endpoints will be described at cluster level.

Individual characteristics will be described between arms to assess for sample representativity and possibly identify imbalances. Since the allocation of clusters between arms is carried out randomly, it is known that any differences that do occur must have occurred by chance. This means that the null hypothesis is known to be true, so there is no logic in testing it. The point of displaying between-arm comparisons is not to carry out a significance test, but to describe in quantitative terms how large any differences were.^{9(p200)}

We will use the findings of the baseline analysis to decide which variables need to be adjusted for in the final analysis.

3.4 STRATEGY OF ANALYSIS

All endpoints in NutriVax intervention will be compared to the standard arm, using appropriate model. No weighting will be applied for the PPS sampling.

3.4.1 Analysis of the primary endpoint:

The primary endpoint is the proportion of children with at least one dose of measles vaccine reported on vaccination card, measured during the endline cross-sectional household survey.

If the children don't have a vaccination card then this endpoint will be considered as failure.

3.4.1.1 *Main analysis first intention:*

In first intention, analysis will be carried out at the individual level, adjusting for clustering and for baseline assessment of outcome in that cluster.

Analysis using the endline cross-sectional household survey will be an individual-level analysis approach, using a logistic regression with random effects (a member of the family of generalised linear mixed model GLMM) with:

- a binomial distribution if the events/trials data syntax is used, or if necessary a binary distribution if an individual-level data syntax is used, depending on adjustments variables if the individual level is necessary or due to problematic of boundary effects with the binomial distribution.^{9(p192),10}
- a logit link function;
- study arm as fixed effect;
- adjustment by cluster level baseline coverage estimate (all patients of a cluster will have the same proportion of vaccination coverage);
- ward (cluster) as random intercept term.

The intervention effect will be estimated as the cluster-specific odds ratio (OR) (with 95% CI) of vaccine between the intervention and the control arm.

The Kenward-Rodger correction¹¹ will be applied to estimate the number of degrees of freedom as it has been shown to improve estimation with a small number of clusters¹²⁻¹⁴.

The ICC at endline will be reported. It will be calculated using the same methods as the ICC at baseline (see chapter 3.1.2). It will also be stratified by study arm.

Additional models will be considered for sensitivity analyses:

- Re-running the same model but without using the Kenward-Rodger correction, using between-within method for DDF¹².

- Model with an additional nested random effect term (LGA : cluster within LGA), or adjusted on LGA as fixed effect.

Adjusted analyses

The logistic regression with random effects will be re-run after adjustment for the individual baseline covariates selected at baseline analysis. We will also adjust on cluster covariates:

- Number of days with no cold chain;
- Number of days of stock of measles vaccines in classes.

It will be performed to identify individual and contextual factors associated with measles vaccine coverage.

3.4.1.2 Main analysis second intention:

In second intention, in case the model does not converge due to low numbers of clusters, we will use the cluster-level analysis. Individual data will be aggregated by cluster as summary statistics for a cluster-level analysis approach with a Student or Wilcoxon test depending on the endpoint distribution to determine the intervention effect.^{9(p197),15}

Assumptions will be verified and alternative approach will be considered in case assumptions are not met.

3.4.1.3 Sensitivity analysis:

We are planning to perform the following two sensitivity analyses:

1) Difference-in-difference (DiD) analysis

To provide a robustness check for the results, a difference-in-difference (DiD) analysis will be performed as an impact analysis.

This DiD analysis calculates the effect of the intervention on the outcome by comparing the average change over time in the outcome variable for the intervention arm to the average change over time for the control arm.

DiD focuses on estimating the average treatment effect by comparing changes over time.

The DiD estimate will be calculated using a logistic regression with the period, the arm and an interaction between period and arm as covariates. We will also adjust on selected covariates. Results of DiD in percentage points (pp) and in relative odds ratio (ROR) (with 95% CI) will be reported.

Should the main analysis and this DiD analysis yield to similar findings, that will increase confidence in the validity of our conclusions.

2) Sub-group analysis

Excluding children aged 21-23 months in the cross-sectional household surveys.

This sensibility analysis is planned because these children could have one dose of measles vaccine, but administered before the intervention period.

3.4.2 Analysis of the main secondary endpoint:

The main secondary endpoint is the measles vaccine coverage, defined as the proportion of children aged 6-12 months at inclusion in the longitudinal follow-up survey, who have received at least one additional dose of measles vaccine, as reported on their vaccination card, administered between inclusion and the end of follow-up.

The original Statistical Analysis Plan planned an individual-level longitudinal mixed-effects logistic regression without a random effect at the patient level, thus not accounting for within-subject correlation that was anticipated in the sample size calculation. Even if a patient-level random effect were introduced, the outcome corresponds to an irreversible event (first additional dose of measles vaccine), resulting in a monotonic outcome pattern over time. In this context, the intra-individual correlation is largely non-identifiable, limiting the interpretability and appropriateness of a longitudinal binary GLMM.

Therefore, the primary analysis will use a time-to-event approach, with time since inclusion as the time scale and a shared frailty term for clusters. This approach provides a statistically valid and clinically interpretable estimate of the intervention effect while appropriately accounting for clustering and censoring.

The time-to-event analysis allows a more informative assessment of the intervention effect by incorporating the timing of vaccination, while preserving the original study objective of improving measles vaccine coverage during follow-up.

For completeness, the following additional analyses will be performed:

- A binary end-of-follow-up analysis (event yes/no at the end of follow-up) will be conducted as a sensitivity analysis for descriptive purposes only.
- A longitudinal repeated binary GLMM with a patient-level random effect will be conducted as a secondary exploratory analysis, acknowledging that the intra-individual correlation is largely absorbed by the monotonic outcome pattern.

These additional analyses are not intended to challenge the conclusions drawn from the primary time-to-event analysis.

This approach ensures consistency between the study design and the statistical methods, while preserving the study objectives, endpoints, and sample size assumptions. The original sample size calculation was based on the cumulative incidence of vaccination during follow-up. The time-to-event analysis targets the same cumulative process while using additional information on the timing of vaccination, and therefore does not compromise statistical power.

This amended Statistical Analysis Plan was finalised prior to database lock and before any comparative analysis was conducted.

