1.6 Study sites

Research and operational activities will take place at community level and in the 20 PHCCs of the 2 LGAs of Karasuwa and Nguru LGAs. Each LGA has 10 wards and there is one PHCC per ward.

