1.7 Randomisation

The unit of randomization (cluster) will be the ward and its catchment area.

Randomization will be stratified by LGA in order to promote balance of the intervention among both LGAs and to give the same opportunity to receive the intervention in both LGAs. Also, the two LGAs may have different populations or contexts that could be a potential confounding factor.

Randomization will be done prior to the baseline survey, because of logistical constraints required for preparing SQ-LNS distribution at health centres (PHCCs), but kept concealed to the data collector until the completion of the baseline survey. After baseline survey completion, the study will be open, as it will not be possible to blind participants or study staff to SQ-LNS supplementation.

In each LGA, the 10 wards will be randomized the same day, by lottery from an envelope, in presence of PHCC department, local community representatives and held in the local language (Hausa). Clusters will be randomly allocated at a ratio of 1:1 either to the standard EPI arm or to the NutriVax arm.

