1.8 SAMPLE SIZE

1.8.1 HHS – primary endpoint

The primary endpoint will be collected among children aged 12-23 months included in the endline HHS about 12 months after the baseline HHS. Based on a baseline measles vaccination (i.e. at least one dose) coverage reported on vaccination card of 30%⁴, a power of 90%, and an intra-cluster correlation of 0.2, an alpha risk of 5%, it will be necessary to include 74 children per cluster. With a rate of unusable data of 5%, we will need 78 children per cluster or a total of 1,560 children to demonstrate a minimum of +10% points difference between the NutriVax and the standard EPI arms, in measles vaccination coverage, i.e. the primary outcome. This calculation was performed using the Shiny CRT calculator used specifically to estimate sample size for cluster randomised trials⁵.

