3.4.2.1 Description

We will describe at each visit, globally and by age classes at inclusion ([6-9[months, [9-12] months):

- proportion of measles vaccine dose 1,
- proportion of measles vaccine dose 2,
- proportion of patients of at least one additional dose of measles vaccine.

For children included at [6-9[months old, measles vaccine dose 1 is supposed to be administered before the first follow-up visit (i.e V1) occurring 4 months after inclusion (i.e M4); measles vaccine dose 2 is supposed to be administered before V2 (M8) if included at [7-9[months old or before V3 (M12) if included at [6-7[months old.

For children included at [9-12] months old, measles vaccine dose 1 is supposed to be administered before inclusion, and measles vaccine dose 2 is supposed to be administered before V1 (M4) if included at [11-12] months old or before V2 (M8) if included at [9-11[months old.

3.4.2.2 Main analysis first intention:

In first intention, analysis will be conducted at the individual level, adjusting for clustering.

A time-to-event approach will be used, where time is defined from inclusion to the first occurrence of an additional dose of measles vaccine. A shared frailty model (Cox proportional hazards model with a random intercept for cluster)^{16,17} will be used to estimate the effect of the intervention.

The intervention effect will be estimated as a hazard ratio (HR) with 95% confidence intervals, comparing the instantaneous risk of receiving an additional dose of measles vaccine between the intervention and control arm, accounting for clustering via the shared frailty term.

For interpretability, the cumulative incidence of vaccination at 12 months will be estimated from the shared frailty Cox model and reported by study arm, together with the absolute difference between arms. Kaplan–Meier curves will be used for descriptive visualization only.

This approach appropriately accounts for clustering, the timing of vaccination, and censoring, and provides a statistically valid and clinically interpretable estimate of the intervention effect.

No adjustment for baseline vaccination status is planned, as the expected number of doses depends on age at inclusion (for children aged 6–9 months at inclusion, 0 dose is expected).

The variance of the shared frailty term will be reported to describe the between-cluster variability.

Adjusted analyses

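### LGA stratifies the randomisation but is missing from the longitudinal Cox model and the fallback tests and is only a sensitivity term for the primary GLMM; if LGA predicts outcome, reported intervals are too wide, chiefly in the longitudinal analysis

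*SAP*

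**What the plan says.** **Design.** SAP section 1.7: "Randomization will be stratified by LGA in order to promote balance of the intervention among both LGAs". It adds that "the two LGAs may have different populations or contexts that could be a potential confounding factor". Section 1.6: "Each LGA has 10 wards and there is one PHCC per ward". Section 1.7: "Clusters will be randomly allocated at a ratio of 1:1". With 10 wards per LGA this means 5 wards per arm in each LGA.

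**Primary endpoint (3.4.1.1).** The main GLMM contains arm, the ward's baseline coverage and a ward random intercept. LGA enters only among the sensitivity models: "Model with an additional nested random effect term (LGA : cluster within LGA), or adjusted on LGA as fixed effect".

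**Main secondary endpoint (3.4.2.2).** "A shared frailty model (Cox proportional hazards model with a random intercept for cluster" is the main model. It has no LGA term, and adjustment for baseline vaccination status is ruled out. The covariates of the adjusted model do not include LGA, and no LGA sensitivity model is listed. Every longitudinal row of Table 2 is analysed in the same way.

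**Fallbacks (3.4.1.2 and 3.4.2.3).** If the model fails to converge, ward summaries are compared by a Student or Wilcoxon test. Neither section mentions LGA or baseline coverage.

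**The concern.** When allocation is balanced within strata, differences between strata cannot contribute to the arm contrast. If the analysis ignores the strata, those differences still count as residual between-ward variation. The reported standard error is then larger than the actual scatter of the estimate, the interval is too wide, and the nominal 5% test rejects less often than 5% under the null.

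This matters here because there are only 20 wards and the planning ICC is 0.2, so between-ward variance dominates the uncertainty. The SAP itself gives a prognostic reason for stratifying. The random-effect form of the sensitivity model is also weak, since a variance component is barely estimable from two LGAs.

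**Working it through.** **1. The plan's own figures.** Section 1.8.1 gives "a power of 90%, and an intra-cluster correlation of 0.2, an alpha risk of 5" per cent, with coverage of 30% against 40% and 20 wards. Take K = 10 wards per arm, mean binomial variance (0.21 + 0.24)/2 = 0.225, and a baseline period with between-period ward correlation 1 (not stated in the SAP).

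- r = 74 × 0.2 / (1 + 73 × 0.2) = 14.8/15.6 = 0.949.
- Variance of the difference = 2 × 0.225 × 15.6 / (10 × 74) × (1 − r²) = 0.00949 × 0.0999 = 0.00095, so SE = 0.0308.
- Power = Φ(0.10/0.0308 − 1.96) = 0.901. Then 74/0.95 = 77.9, rounded up to 78, and 78 × 20 = 1,560. This agrees with the SAP.
- Longitudinal: m = 28 with individual autocorrelation 0.5 gives r = (5.6 + 0.4)/6.4 = 0.9375, SE = 0.0353 and power 0.809. Then 28/0.95 = 29.5, rounded up to 30, and 30 × 20 = 600. This agrees with the SAP.

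Neither figure depends on LGA.

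**2. How large an LGA effect is being assumed.** Between-ward variance is 0.2 × 0.225 = 0.045. If LGA explains a share s of it, the gap between LGAs is 2√(0.045s): 13, 21 and 30 percentage points for s = 10, 25 and 50%. The SAP gives no figure, so s is an assumption.

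**3. Longitudinal analysis, no baseline covariate.** Ward-level simulation (linear model on ward proportions, 5 against 5 wards per LGA, t reference):

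| LGA share | Mean SE without LGA | Mean SE with LGA | Inflation | Type I error without LGA | Power for +10 points, without / with LGA |
|---|---|---|---|---|---|
| 0 | 0.1000 | 0.0998 | about 0% | 0.055 | 0.14 / 0.15 |
| 10% | 0.1009 | 0.0958 | 5% | 0.040 | 0.14 / 0.16 |
| 25% | 0.1013 | 0.0881 | 15% | 0.028 | 0.12 / 0.19 |
| 50% | 0.1027 | 0.0750 | 37% | 0.008 | 0.08 / 0.25 |

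The 0.055 in the first row is the nominal 5% within simulation error.

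A closed-form check at s = 25% with 28 children per ward:

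- Ward variance within an LGA is 0.045 × 0.75 + 0.18/28 = 0.0402.
- The squared half-gap is 0.045 × 0.25 = 0.01125.
- Omitting LGA gives an expected mean square of 0.0402 + (20/18) × 0.01125 = 0.0527.
- √(0.0527/0.0402) = 1.145, in line with the simulated 15%.

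At s = 50% the standard deviation of the estimate was 0.0754 with and without LGA. Only the reported SE changed.

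**4. Primary model, ward baseline coverage included.** Mean SE without / with LGA:

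| LGA share | Between-period ward correlation 0.9 | Between-period ward correlation 0.7 |
|---|---|---|
| 0 | 0.0513 / 0.0513 | 0.0736 / 0.0736 |
| 10% | 0.0494 / 0.0494 | 0.0710 / 0.0705 |
| 25% | 0.0470 / 0.0469 | 0.0666 / 0.0654 |
| 50% | 0.0426 / 0.0421 | 0.0580 / 0.0557 |

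The largest ratio is 0.0580/0.0557 = 1.04. Type I error without LGA is 0.046 to 0.050.

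**5. If the LGAs diverge during the year.** Baseline coverage cannot absorb a new gap. If the gap shifts by 5, 10 or 15 points (assumed), the primary SE is inflated by about 3, 10 or 22% at correlation 0.9, and about 1, 5 or 11% at 0.7.

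**Limit.** All of this is a linear ward-level approximation to the logistic and Cox models.

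**The case against.** **The loss is conditional.** This stands. If LGA does not predict outcome, nothing is lost. The SAP says only that the LGAs may differ, and the 50% case needs a 30-point gap that nothing in the document supports.

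**The primary endpoint is largely covered.** This mostly stands. A reader might apply the simple factor 1/√(1 − R²) to the primary GLMM and infer inflation of 5, 12, 20 or 41% for R² of 10, 20, 30 or 50%, with type I error down to 0.9%. The documents do not support that reading. Type I errors obtained by comparing t on 18 and 17 degrees of freedom belong to an arm-only model, whereas section 3.4.1.1 also fits ward baseline coverage. R² would have to be the share of variance left after that adjustment. The 4% found above corresponds to a remaining share of 1 − 1/1.04² = 8%, below even the lowest of those cases. An LGA fixed-effect model is also already among the planned sensitivity analyses, and section 3.3 lets baseline findings guide adjustment.

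**The error is conservative.** This stands. A reader might infer a biased comparison or a false-positive risk. With wards balanced within each LGA, neither follows from this omission.

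**What the objection leaves untouched.** In the longitudinal Cox analysis nothing absorbs an LGA difference and no LGA sensitivity model is planned. The fallback tests have the same gap. If the GLMM failed to converge, the primary endpoint would be tested with neither LGA nor baseline coverage.

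**Conclusion.** The point holds in conditional form. The stratification factor is absent from the main longitudinal model and from the fallback tests, and it is secondary in the primary analysis. To the extent that LGA predicts outcome, reported intervals are wider than they need be and tests are conservative.

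The effect falls chiefly on the longitudinal analysis and the Table 2 endpoints that share its method, where inflation runs from nothing to about 37% over the assumed LGA shares. For the primary GLMM it is a matter of a few per cent at most, unless the LGAs move apart between the two surveys. The direction is firm. The sizes rest on assumed LGA shares, assumed between-period correlations and the linear approximation.

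**What to change.** - **3.4.2.2:** include LGA as a fixed effect or stratum in the Cox frailty model, and so in the Table 2 rows that refer to that section.
- **3.4.1.1:** include LGA as a fixed effect in the main GLMM. Keep the model without LGA as the sensitivity analysis and delete the LGA random-effect option.
- **3.4.1.2 and 3.4.2.3:** stratify the cluster-level fallback tests by LGA.

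**Cost:** SAP wording, one model term and one between-ward degree of freedom. That is about 17 to 16 in the primary model (two-sided 5% t value 2.110 to 2.120) and 18 to 17 where there is no baseline covariate (2.101 to 2.110).

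Section 3.4.2 records that the amended SAP was finalised before database lock and before any comparative analysis. This change should be made on the same footing, because choosing the LGA model after seeing results would not be credible.

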2.3.2 Type I error

We will use a two-sided type I error α of 5% to compare endpoints between arms without any correction for multiple comparisons.

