In second intention, in case the model does not converge due to low numbers of clusters, we will use the cluster-level analysis. Individual data will be aggregated by cluster, and cluster-level summary statistics (e.g., cumulative incidence of vaccination at 12 months or median time to event) will be calculated. Intervention effects will then be compared between arms using appropriate statistical tests (Student's t-test or Wilcoxon rank-sum test), depending on the distribution of cluster-level summaries.

Assumptions will be verified and alternative approach will be considered in case assumptions are not met.

3.4.2.4 *Additional analyses :*

For completeness, the following additional analyses will be performed to provide descriptive and exploratory insights, without challenging the primary time-to-event results:

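### If the primary model does not converge, the fallback test drops the ward baseline-coverage adjustment on which the stated sample size rests

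*SAP*

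**What the plan says.** The first-intention analysis of the primary endpoint (SAP 3.4.1.1) is a logistic model with a random intercept for ward, a fixed effect for arm, and "adjustment by cluster level baseline coverage estimate (all patients of a cluster will have the same proportion of vaccination coverage").

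Section 3.4.1.2 provides for that model failing to converge because there are few clusters. The data are then aggregated by ward as "summary statistics for a cluster-level analysis approach with a Student or Wilcoxon test depending on the endpoint distribution". The section names no baseline covariate, change score or baseline-adjusted residual. It adds only that some other approach, not described, will be considered if assumptions are not met. The difference-in-difference analysis in 3.4.1.3 does use the baseline survey, but as a sensitivity analysis and not as the replacement for the primary model.

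The sample size (1.8.1) assumes "coverage reported on vaccination card of 30"%, aims "to demonstrate a minimum of +10% points difference between the NutriVax and the standard EPI arms", and uses "a power of 90%, and an intra-cluster correlation of 0.2, an alpha risk of 5"%. It concludes that "it will be necessary to include 74 children per cluster".

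**The concern.** A prespecified fallback should answer the same question as the analysis it replaces. Student and Wilcoxon tests are two-sample tests with no place for a covariate, so a purely numerical failure would turn a baseline-adjusted comparison into an endline-only one. With 10 wards per arm and the between-ward variation implied by an ICC of 0.2, chance imbalance in baseline coverage is a main source of error in the estimate, and the baseline term is there to remove it. If the sample size was set on the assumption that baseline coverage would be used, the fallback cannot have the power the trial was planned for.

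**Working it through.** **Inputs.** From 1.8.1: 30% against 40%, ICC ρ = 0.2, m = 74 evaluable children per ward, 90% power. From 1.6 and 1.7: 20 wards allocated 1:1, so k = 10 per arm. From 2.3.2: "We will use a two-sided type I error α of 5% to compare endpoints between arms".

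**Assumptions.** The SAP gives no ward correlation over time (cluster autocorrelation, CAC) for the household surveys, so a range is shown. The baseline survey is taken to have the same number of children per ward as the endline survey.

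**Formulas**
- Design effect without baseline: DE = 1 + (m − 1)ρ
- Correlation of a ward's baseline and endline proportions: r = mρ·CAC / DE
- Design effect with baseline adjustment: DE × (1 − r²)
- SE of the difference: √{(0.3×0.7 + 0.4×0.6) × design effect / (k·m)}, with 0.21 + 0.24 = 0.45

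**Step 1: reproduce 74 per ward.** With CAC = 1:
- DE = 1 + 73×0.2 = 15.6
- r = 14.8/15.6 = 0.949
- DE(1 − r²) = 1.559
- SE = √(0.45×1.559/740) = 0.0308, so 0.10/SE = 3.248

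Normal-approximation power is 90.1% at m = 74 and 89.7% at m = 73, so 74 is the smallest size that reaches 90%. Then 74/0.95 = 77.9, which gives 78 per ward, and 78×20 = 1,560, as the SAP states.

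**Step 2: try to reproduce it without baseline.** As m grows, the SE falls no lower than √(0.45×0.2/10) = 0.0949. Power is then capped at about 18% (normal) or 17% (t, 18 df) however many children are sampled. No ward size reaches 90%.

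**Step 3: power of the fallback at 74 per ward.** Design effect 15.6, effective sample 740/15.6 = 47.4 per arm, SE = √(0.45×15.6/740) = 0.0974. The noncentral t with 18 df gives 16.3%. Simulation gives 16.3% for the t test and 14.1% for the Wilcoxon test.

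**Step 4: ward-level regression on arm and baseline coverage (17 df)**

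| CAC | r | Design effect | SE | Power |
|---|---|---|---|---|
| 0.5 | 0.474 | 12.09 | 0.0857 | 20% |
| 0.8 | 0.759 | 6.61 | 0.0634 | 32% |
| 0.9 | 0.854 | 4.23 | 0.0507 | 46% |
| 0.95 | 0.901 | 2.93 | 0.0422 | 61% |
| 1.0 | 0.949 | 1.56 | 0.0308 | 86% |

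The last row is below 90% because it uses 17 df and not the normal approximation. Simulation at CAC = 1 gives 83%. Adding LGA (16 df) costs less than 0.4 points in every row, before any credit for variance that LGA explains.

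**Step 5: lower ICC (74 per ward)**

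| ICC | Endline-only t test | Adjusted, CAC 0.8 to 1.0 |
|---|---|---|
| 0.2 | 16% | 32% to 86% |
| 0.1 | 27% | 47% to 83% |
| 0.05 | 43% | 63% to 83% |

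**The case against.** **The trigger may be remote.** The model has a single random intercept over 20 wards of about 74 children, and 3.4.1.1 already allows a change of data syntax for boundary problems. In 300 simulated trials at the planning inputs, the model converged every time. This stands: the power loss is conditional, and other software may behave differently. But the SAP itself foresees non-convergence and makes this test the main analysis if it occurs.

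**The size depends on inputs that are not settled.** This also stands. The CAC is not stated, and at 0.5 the gain from adjustment is only 3 to 4 points. Sections 1.8.3 and 3.1.2 say the ICC will be re-estimated from the baseline survey. A reader might infer that the fallback always takes power from 90% to 16%. The documents support that contrast only at ICC 0.2 with a CAC of 1.

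**Three stronger readings are not supported.**
- The longitudinal fallback in 3.4.2.3, where "Intervention effects will then be compared between arms using appropriate statistical tests", might seem to have the same gap. It does not. Section 3.4.2.2 deliberately plans no adjustment for baseline vaccination status, because the doses expected depend on age at inclusion, so that fallback drops nothing.
- LGA is not lost in the fallback. In 3.4.1.1 it appears only in a sensitivity model.
- The lack of a percentage-point estimate is not peculiar to a Wilcoxon fallback. The first-intention model reports an odds ratio, and the difference-in-difference analysis gives percentage points in either case.

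**The endline-only comparison is still randomised.** This is true, so the issue is precision and consistency with the planned analysis. It is not systematic bias.

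**Conclusion.** The point holds for section 3.4.1.2 only. The fallback omits an adjustment that the first-intention model makes and without which the stated sample size cannot be obtained. If it is used at the planning inputs, power is about 16%. Keeping ward baseline coverage is better at every CAC examined from 0.5 to 1.0, by a margin that runs from a few points to about 70 (86% against 16%).

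These figures rest on non-convergence occurring, on the planning ICC of 0.2, on a CAC that is inferred from the reproduced sample size and not stated, and on equal baseline and endline ward sizes. The direction of the advantage does not change across the ICC and CAC values shown. Its size does.

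**What to change.** In 3.4.1.2, replace the Student or Wilcoxon test with a linear regression of the 20 endline ward proportions on arm and ward baseline coverage, and report the adjusted difference with a t-based 95% CI. Logits of the proportions are an acceptable alternative outcome. LGA may be added as the randomisation stratum. The SAP should fix the outcome scale and the use of LGA in advance. Leave 3.4.2.3 unchanged on this point.

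The cost is one SAP paragraph and one degree of freedom relative to the two-sample t test (18 to 17), or two with LGA (16). No new data are needed, since ward baseline coverage is already to be calculated under 3.1.2.
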